1. SUMMARY

1.1 SYNOPSIS

Title:	Satiety and transdermal alcohol concentration (SatTAC)
Study Description:	The proposed study is an inter-lab collaboration to gather pilot data on responses to alcohol in a controlled laboratory setting compared to a naturalistic setting. Alcohol is administered in the lab and alcohol exposure is measured with a wearable wrist monitor (Skyn) and a breathalyzer (BACtrack S80). Naturalistic drinking and alcohol-related harms are assessed during a 7-day remote assessment period. Additional aims assessed during laboratory visits include changes in satiety to alcohol after dietary manipulation and the relationship between responses to alcohol and biomarkers: GLP-1 and HMGB1.
Objectives:	
Aim 1: Identify the correlations between transdermal alcohol concentration (TAC; Skyn) and breath alcohol concentration (BrAC; BACtrack S80) in controlled laboratory and natural settings and compare correlations across settings.
 
Aim 2: Compare TAC and BrAC as predictors of self-reported number of drinks consumed and the odds and frequency of alcohol-related harms in natural settings.
 
Aim 3: Model individual differences in alcohol-specific satiety using self-report and a paced-drinking alcohol administration laboratory model.
 
Aim 4: Assess the effect of a dietary supplement on plasma GLP-1 levels and subjective and alcohol satiety.
 
Aim 5: Assess the effect of acute alcohol exposure on a marker of peripheral inflammation (HMGB1)

Outcomes:	
Alcohol exposure: Transdermal alcohol concentration, breath alcohol concentration. Questionnaires: Self-reported satiety questionnaire and other alcohol subjective response questionnaires. Tasks: Behavioral economic demand for alcohol, attentional bias to alcohol-related cues. Remote self-reported assessment of alcohol-related harms. Biomarkers: Plasma change in GLP-1 and HMGB1.

Study Population:	Adults from the triangle area (Chapel Hill, Raleigh, Durham) who meet NIAAA criteria for at-risk drinking; >7/14 standard drinks per week for women/men, with at least one past-month heavy drinking episode defined as 4/5+ standard drinks for women/men.
Description of Sites/Facilities Enrolling:	University of North Carolina at Chapel Hill
Participants:	55
Study Duration:	1 year
Participant Duration:	Each participant completes an online pre-screen eligibility survey, virtual visit, and two 5-6 hour lab visits within 2-3 days of one another, followed by a 7-day remote assessment period, and a final 1-hour discharge visit.

1.2 SCHEDULE OF ACTIVITIES (SOA)

Procedures	Online Prescreen	Virtual Visit	Study visit 1	Study Visit 2	7 day Remote Assessment	Discharge visit
Online prescreen survey	X					
Informed consent		X				
DSM-5 SCID AUD and SUD		X				
Demographics Form		X				
Alcohol Use Identification Test (AUDIT)		X				
Inventory of Drinking Situations (IDS)		X				
Obsessive Compulsive Drinking Scale (OCDS)		X				
Reward-based Eating Drive Scale (RBEDS)		X				
Body Perception Questionnaire (BPQ)		X				
Drinking Motives Questionnaire (DMQ)		X				
Comprehensive Relative Autonomy Index for Drinking (CRAI Drinking)		X				
Alcohol Sensitivity Questionnaire (ASQ)		X				
Impaired Control Scale (ICS)		X				
Dietary supplement or placebo			X	X		
Administer alcohol priming drink			X	X		
Paced alcohol or control drinking			X	X		
Weight and height			X			
Pregnancy test			X	X		
Alcohol-specific satiety questionnaire			X	X		
Drug Effects Questionnaire (DEQ)			X	X	X	
Visual Analogue Scale (VAS)			X	X		
Biphasic Alcohol Effects Scale (BAES)			X	X		
Subjective Effects of Alcohol Scale (SEAS)			X	X		
Alcohol Urge Questionnaire (AUQ)			X	X		
Alcohol Purchase Task (APT)			X	X		
Dot Probe task			X	X		
Breath Alcohol Concentration (BrAC)			X	X	X	
Transdermal Alcohol Concentration (TAC), measured via Skyn			X	X	X	
Ecological Momentary Assessment (EMA)					X	
DEXA scan					X	
Venipuncture blood sample x2			X	X		
Fingerprick blood sample x3			X	X		
Timeline followback (TLFB)						X
Brief young adult alcohol consequences questionnaire						X
Importance of consequences of drinking short-form						X
Return Skyn monitor						X

2. INTRODUCTION

2.1 STUDY RATIONALE

Alcohol response can indicate differential risk for heavy drinking and the development of alcohol use disorder. Laboratory and naturalistic methods of data collection on acute responses to alcohol may be used in a complementary way to assess alcohol risk phenotypes. Satiety to the effects of alcohol is an understudied and ill-defined construct which may confer protective effects for heavy drinking. Satiety related hormones like glucagon-like peptide 1 (GLP-1) and the inflammatory biomarker, high-mobility group box 1 (HMGB1) may represent biomarkers of alcohol use disorder risk. However, researchers currently have a limited ability to accurately and non- invasively assess individuals' real-time alcohol use exposure. Transdermal alcohol concentration (TAC) sensors and ecological momentary assessment may be used to address this gap. Furthermore, it is not well understood how naturalistic alcohol data collection methods relate to drinking in a controlled laboratory setting. In an inter-lab collaboration TAC will be measured during both laboratory and naturalistic drinking contexts to assess the strength of the association between a novel TAC sensor (BACtrack Skyn) and breath alcohol (BrAC) measurements. Alcohol-specific satiety will be measured during alcohol drinking lab sessions and the biomarkers, GLP-1 and HMGB1 will be assessed as potential biomarkers of satiety and heavy drinking risk.

2.2 BACKGROUND

Introduction

Over half of U.S. adults consumed some alcohol in the past month, with 37% of college and 29% of non-college young adults ages 18-25 engaging in binge drinking (5/4+ drinks for men/women).[1] Many young adults also exceed binge drinking thresholds, with 1 in 20 consuming 10+ drinks and 1 in 33 consuming 15+ drinks during a single drinking bout.[2, 3] These excessive drinking behaviors increase risk for a multitude of severe acute consequences, including physical and sexual assault, hospitalization and death, hangovers, and cognitive impairment.[4-6] Long-term consequences of excessive drinking include alcohol dependence and risk of cancer and fatty liver disease. [5, 7, 8] Despite the significant public health burden associated with the short- and long-term harms of excessive alcohol use, researchers currently have a limited ability to accurately and non- invasively assess individuals' real-time alcohol use exposure. Accurately and non-invasively assessing real-time alcohol use exposure has the potential to inform just-in-time harm reduction interventions.

Transdermal Alcohol Concentration Sensor

The majority of research capturing real-time alcohol use exposure relies on participant self-reports or obtrusive alcohol sensors. Self-report is commonly criticized due to social desirability biases and the difficulty of accurately estimating drink volume and ethanol content,[9-12] is limited by the neuro-cognitive effects of alcohol, especially with excessive drinking, and [13] is burdensome for participants [12]. In contrast to self-report, wearable alcohol sensors enable continuous assessment of real-time biological alcohol exposure via transdermal alcohol concentration (TAC), an indirect index of blood and breath alcohol concentration (BAC and BrAC, respectively), which are typically assessed via breathalyzer.

Breathalyzer measurement of BAC or BrAC requires frequent repeated measures that may be too burdensome and invasive for participants [14-17]. In contrast, TAC sensors provide a mostly passive and non-invasive approach for continuously monitoring alcohol exposure. TAC sensors are worn on the ankle or wrist and measure the 1% of alcohol that is eliminated through the skin via insensible perspiration or sweat [16, 18-21]. One limitation of TAC is that it is not quantitatively equivalent to BAC or BrAC. TAC reflects an individual's relative alcohol exposure, whereas BAC/BrAC reflect absolute alcohol exposure, which provides actionable information about a person's likely level of cognitive and physical impairment due to alcohol use [18, 22]. Unfortunately, there are currently no reliable methods for directly estimating BAC from TAC, due to the variety of factors that can impact individual differences in TAC (e.g., sex, age, fat-free mass, skin temperature) [15, 21-26]. Translating TAC to BAC/BrAC is necessary prior to leveraging wearable TAC sensors to provide actionable knowledge to inform just-in- time harm reduction interventions. The most unobtrusive and user-friendly TAC sensor currently in use is the BACtrack Skyn (Skyn). The Skyn is a small, lightweight wrist-worn sensor that collects TAC data every 20 seconds and that participants are comfortable and willing to wear across extended time periods in natural settings [14-17, 22, 27-30]. The few studies testing the Skyn under controlled laboratory conditions suggest that Skyn TAC values strongly correlate with BrAC [15] and can be used to estimate BAC at low or moderate BAC levels [31]. However, it is often infeasible and unethical to dose participants in laboratory settings to the excessive levels they dose themselves in natural settings. Additionally, laboratory studies preclude examining whether TAC values predict next-day alcohol-related harms, such as hangovers or blackouts. While two studies have compared the Skyn to another commonly-used TAC sensor in natural settings and found moderate-to-strong correlations between the sensors, [27, 30] we are unaware of any studies comparing the Skyn to BAC or BrAC in natural settings or of any studies examining TAC relative to BrAC as a predictor of volume of consumption and alcohol-related harms (e.g., sickness, hangover). As such, it remains unclear whether correlations between Skyn TAC values and BrAC captured in controlled laboratory settings translate to alcohol use in real-world settings or whether TAC values perform similarly to BrAC in predicting next-day alcohol-related harms [17, 22, 27, 31].

Alcohol-specific satiety and GLP-1

While laboratory settings do not allow for dosing at the levels of natural settings, the laboratory setting provides a controlled context in which to verify the precise level of alcohol exposure, and to experimentally test the effects of alcohol on a person's internal state. The internal state plays an important role in regulating the incentive value of a reward, with satiety being a prime example of a motivational state which reduces reward-value and appetitive motivation [32-35]. Satiety is fundamental in regulating food intake, and resistance to satiety has been implicated in obesity-related overeating behavior [36]. Satiety in the context of drug and alcohol consumption is understudied, despite overlapping mesolimbic neurocircuitry involved in appetitive motivation for both food and drugs [37]. Observations from human lab studies suggest that a dose of alcohol can either prime further alcohol consumption or promote satiety, indicated by reductions in the desire to drink and attentional bias to alcohol-related cues [38, 39]. However, an alcohol-specific satiety construct has yet to be the subject of rigorous investigation. Resistance to satiety may be implicated in the binge-like consumption behavior symptomatic of alcohol and substance use disorder (A/SUD), warranting investigation of satiety-promoting factors.

Glucagon-like peptide 1 (GLP-1) is an incretin hormone that increases subjective satiety and reduces food consumption [40] in part through inhibition of accumbal dopamine release [41], implicating

incentive motivation in GLP-1 satiety signaling. Through the same mechanism, GLP-1 receptor agonists (GLP-1RAs) reduce consumption of alcohol and other drugs in animal models [42, 43], making GLP-1RAs promising candidates for AUD pharmacotherapy [44]. An analysis of social media reports from our lab indicate that some patients prescribed GLP-1RAs for obesity or type-2 diabetes report reduced desire for alcohol and changes in subjective response which indicate increased satiety i.e. being satisfied with fewer drinks, reduced interest or desire for alcohol [45]. Alcohol-specific satiety may be a translational mechanism by which GLP-1 receptor agonists reduce alcohol consumption. However, alcohol-specific satiety as a construct has not been modeled in the laboratory.

Inflammation and HMGB1

Increasing evidence also suggests that chronic alcohol consumption promotes neuroinflammation. Increases in systemic inflammation due to alcohol consumption are proposed to contribute both to alcohol-related diseases (including liver disease and cancers) and negative affective states in AUD (e.g., pain, stress). Examination of postmortem human brain tissue demonstrates increased proinflammatory signaling molecules in AUD – one such marker being high-mobility group box 1 (HMGB1) [46, 47]. Evidence from both human and animal brain tissue shows that HMGB1 is a key marker of alcohol-induced immune activation [46-51].

Summary

The goal of the proposed study is to collect pilot data on factors which may predict risk for alcohol use disorder through an inter-lab collaboration using data from 2 alcohol drinking laboratory visits and a 7-day remote assessment period. Correlations between Skyn TAC and BrAC will be assessed in an internally valid, controlled laboratory setting and in an ecologically valid natural setting within the same individuals, and to examine correspondence between TAC and BrAC in predicting alcohol consumption and alcohol-related harms among 42 moderate-heavy drinking adults. During laboratory sessions, additional aims related to individual differences in alcohol risk phenotypes will be assessed. Satiety to the effects of alcohol will be assessed using a novel self-report measure of alcohol-specific satiety and a laboratory model of paced drinking, and the effect of a GLP-1 stimulating dietary supplement on alcohol-specific satiety. In addition, individual differences on an inflammatory biomarker, HGMB1 on drinking outcomes will be assessed.

2.3 RISK/BENEFIT ASSESSMENT

2.3.1 KNOWN POTENTIAL RISKS

Risk of Confidentiality Breach: To avoid breaches in confidentiality, study documents that contain personal information and including the informed consent document are kept in locked filing cabinets in locked rooms separate from any source documents containing participant dummy identifiers. The document that links study ID numbers to personal identifying information is encrypted and protected using a password-protected document on a secure server provided by UNC Department of Psychology and Neuroscience. All data is stored in locked cabinets inside locked offices; electronic data will be stored only on password-protected computers. Only study personnel will have access to the data. All study staff participate in

annual human participant training that includes education about responsibilities to the minimize risk of confidentiality breach. All patient identifiers will be stored in REDCap (or similar platform) until recruitment is over. When recruitment is over, all patients who do not consent or are not eligible for participation in the study will have their responses permanently deleted.

Risk of Embarrassment: Self-report assessments contain questions regarding sensitive personal information. This risk is necessary to assess psychological symptoms. Participants will be informed that they can decline to answer any survey questions that they're uncomfortable with by selecting '*Prefer not to answer*'. Participants will be assured upon intake that only study personnel will have access to study data, which will not be stored with any self-identifying information. Embarrassment and/or emotional distress may occur with the measurement of body composition, but this is rare (<1%). To minimize this risk, participants will be measured individually, with no one but the trained research staff present, in a private area.

Risk from Participation in Alcohol Administration Sessions: Other potential risks include typical risks related to participation in alcohol administration studies. For example, it is possible that participants may experience dizziness/nausea from drinking during these visits, or symptoms the following day (e.g., headache). Our group has considerable experience with alcohol administration procedures [80-84], and the safety precautions required in these studies. Across these studies, the incidence of adverse events such as vomiting has been exceptionally low. Our procedures will follow the NIAAA recommended guidelines for administering alcohol to human subjects (<https://www.niaaa.nih.gov/Resources/ResearchResources/job22.htm>). Briefly, the NIAAA guidelines include recommendations for administering alcohol to participants who meet criteria for AUD. In particular, we have taken measures to protect against ethical concerns by *excluding treatment-seekers* (or those engaged in an active quit attempt), as per the NIAAA recommended guidelines. Additionally, we will screen out participants with severe AUD (defined as 6 or more of 11 symptoms). This approach allows us to generate data relevant to a clinical population while minimizing risks.

Risk from Dietary supplements: There is the infrequent and mild potential risk of gastrointestinal discomfort associated with dietary fiber and green tea extract supplements. To minimize these risks, effective doses of each supplement have been chosen which have been shown to be safe and tolerable for human subject research in prior studies [52, 53].

Risk from blood draws: There is a rare (<1%) risk of infection following blood draws. Trained personnel will conduct all procedures and the site of blood draws will be cleaned appropriately prior to data collection.

Potential physical risks: During the dual x-ray absorptiometry scan (DEXA) subjects will be exposed to very low doses of radiation. The amount of x-ray radiation that subjects will receive during the scan is approximately 0.8 mrems, which is extremely small. The amount of radiation is less than one tenth of the amount used during a normal chest X-ray and significantly less than the radiation received from natural background in a year (300 mrem).

2.3.2 KNOWN POTENTIAL BENEFITS

This study has not been designed to benefit the individual participants. However, the knowledge gained from this study will contribute to understanding about the psychological and biological basis of substance use disorder which may be used to develop future interventions. All participants will receive feedback regarding anthropometric and body composition measures.

2.3.3 ASSESSMENT OF POTENTIAL RISKS AND BENEFITS

The risks and benefits presented above are no more serious than for other observational studies in this population. Based on the need to discover mechanisms contributing to AUD, the potential risks outweigh the potential benefits.

3. OBJECTIVE AND OUTCOME MEASURES

Aim 1: Identify the correlations between transdermal alcohol concentration (TAC) and breath alcohol concentration (BrAC) in controlled laboratory and natural settings and compare correlations across settings.

- Outcomes measures: BrAC using the BACtrack S80 and TAC readings using the BACtrack Skyn monitor and light-based finger monitor during laboratory alcohol drinking sessions and a remote assessment period.

Aim 2: Compare TAC and BrAC as predictors of self-reported number of drinks consumed and the odds and frequency of alcohol-related harms in natural settings.

- Outcome measures: BrAC and TAC readings, self-reported number of drinks and alcohol related harms measured using a mobile app questionnaire (LifeData app).

Aim 3: Model individual differences in alcohol-specific satiety using self-report and a paced-drinking alcohol administration laboratory model.

- Outcome measures: Alcohol specific satiety questionnaire, BrAC readings.
- Secondary measures: Self-report alcohol subjective effects (stimulation, sedation, craving), behavioral economic demand for alcohol, attentional bias for alcohol related cues.

Aim 4: Assess the effect of a dietary supplement on satiety to alcohol

- Outcome measures: Blood plasma GLP-1 levels samples during lab sessions via venipuncture before and after supplement administration, alcohol-specific satiety questionnaire

Aim 5: Assess the effect of alcohol exposure on HMBG-1 marker of inflammation

- Outcome measures: Blood plasma levels of HMBG-1 will sampled during lab sessions via fingerprick at timepoints before alcohol administration, 30 minutes after an initial priming drink, and after the final drink.

4. STUDY DESIGN

4.1 OVERALL DESIGN

Study Design and overview: Aims related to alcohol response will be assessed using alcohol administration in the laboratory. Additional aims related to naturalistic drinking and alcohol related harms will be gathered using wearable alcohol sensors and ecological momentary assessments (EMA) and daily diaries. Transdermal alcohol concentration (TAC) will be measured during both laboratory and

naturalistic drinking contexts to assess the strength of the association between a novel TAC sensor (BACtrack Skyn) and breath alcohol (BrAC) measurements. In addition, we will also use a small non-intrusive light-based blood flow measurement device (placed on the participant's finger) and validate these measurements against the other metrics. These aims will be accomplished using data from two half-day visits to our lab at UNC campus, 1-2 days apart, followed by a 7-day remote assessment study and a final brief discharge visit (Figure 1). Lab visits involve a novel self-report questionnaire to assess alcohol-specific satiety during a paced alcohol challenge paradigm. In addition, on each of the two sessions in counterbalanced order, participants receive either a dietary supplement intended to stimulate postprandial GLP-1, or a calorically matched placebo to assess the effect of GLP-1 stimulation on alcohol-specific satiety. Two blood samples will be collected at each session to confirm plasma levels of glucagon-like peptide 1 (GLP-1). Blood fingerprick samples will be used to measure high-mobility group box 1 (HMGB1) inflammatory marker at three timepoints after alcohol administration. Additional measures of reward and incentive motivation for alcohol will be included to test the hypothesis that satiety is associated with reduced incentive motivation for alcohol reward. At the end of the second lab visit participants will be oriented to the 7-day remote assessment study. During the 7-day remote visit participants will be asked to wear the Skyn sensor continuously across 24-hours/day, except when bathing/showering or charging the device, and to initiate EMAs if they start an alcohol drinking bout. During drinking bouts, and for up to one hour following drinking bouts, participants will be prompted to record their BrAC every 20 minutes and to self-report the number of drinks consumed since the prior survey and subjective intoxication. Each morning, participants will complete daily diaries reporting alcohol-related harms experienced on the prior day. Following the 7-day remote visit, participants will complete a final discharge visit to return study devices, complete a timeline follow-back, and undergo a dual x-ray absorptiometry (DEXA) scan to assess fat-free mass, which will be included as a covariate in subsequent analyses to account for alcohol-elimination rate [56]..

[figure not shown]

Figure 1. Diagram of lab session procedures

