4.3 STUDY VISIT PROCEDURES

Participants will arrive to the lab at 9 AM fasted overnight prior to the alcohol administration study visits. Identity will be confirmed by verification of photo ID and pregnancy will be confirmed with a urine pregnancy screen. Abstinence from alcohol will be confirmed with a breathalyzer. Mode of transportation to the session will be confirmed. Participants will be encouraged to arrange for a ride or take public transportation to sessions to minimize the risk of driving while intoxicated. In the case that a participant drives themselves to the session, the participant will be required to sign an acknowledgment that their keys will be held by the research assistant during the session and returned after the subject's BAC reaches zero. Blood will be sampled with venipuncture to analyze baseline plasma GLP-1. Fingerprick blood sample will be used to measure HMGB1. Baseline measurements of study outcomes will be taken at this time. Participant will complete additional baseline measures at home including: demographics form, the Alcohol Use Disorder Identification Test (AUDIT) [57], Obsessive Compulsive Drinking Scale (OCDS) [58], Reward-based Eating Drive Scale (RBEDS) [59], Body Perception Questionnaire (BPQ) [60], Drinking Motives Questionnaire (DMQ) [61], Comprehensive Relative Autonomy Index for Drinking (CRAI Drinking) [62], Alcohol Sensitivity Questionnaire (ASQ) [63], and the Impaired Control Scale (ICS) [64], and the Inventory of Drinking Situations (IDS) [65] using REDCap to explore potential moderators in secondary analyses. Assessments will occur in a study room furnished to feel like a comfortable living room with a TV. Participants may watch TV or engage in relaxing recreational activities (e.g. reading, personal computer) during recovery from alcohol. Participants will be fitted with a Skyn TAC wrist monitor and finger-tip sensor to monitor alcohol exposure and be trained on using the BACtrack S80 for BrAC measures. Participants will download the Skyn app to sync the Skyn data during the session, and then will be instructed to refrain from using their phones for non-study related purposes.

Dietary manipulation

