Participants will receive a beverage containing either a dietary supplement (10g Fibersol®-2 mixed with water and aspartame sweetener for taste + 725mg decaffeinated green tea extract capsule) or a calorically matched placebo supplement (Aspartame sweetener mixed with water + aspartame capsule) counterbalanced at two separate visits. Forty-five minutes after the dietary supplement, the second blood sample is taken. Next, a priming drink (calculated to achieve 30mg% BAC) is administered to stimulate craving for alcohol [66, 67]. Drinks will consist of 40 proof vodka and a sugar-free cranberry juice mixer at a 1:5 ratio. Doses are calculated to achieve target BACs based on sex and body weight using formulas established in prior research [68]. Fifteen minutes after the priming drink, a novel alcohol-specific satiety questionnaire will be administered followed by alcohol incentive motivation tasks (alcohol purchase task; APT [69], dot probe attentional bias to alcohol-related stimuli), additional validated alcohol subjective response questionnaires (Drug Effects Questionnaire; DEQ[70], Biphasic Alcohol Effects Scale; BAES [71], Alcohol Urge Questionnaire; AUQ [72], Subjective Effects of Alcohol Scale; SEAS [73]), *hunger, fullness, and satiety* visual analogue scale (VAS) items, a BACtrack S80 BrAC measure, and a fingerprick blood sample.

Alcohol-specific satiety paced drinking procedure

Then over a 2-hour period, 5 additional mini-drinks (calculated to achieve an estimated BAC increase of 10mg% each or placebo) are administered with 15 min absorption time between each drink to reach an estimated maximum BAC of 60-70mg%, reflecting a moderate level of alcohol exposure (80mg% is the conventional cutoff for “binge” exposure). Participants have 3 minutes to finish each drink (Average volume of a drink, alcohol+mixer at a 1:5 ratio is 8/5oz for a man/woman). This paradigm is designed to approximate a natural drinking pace, while controlling for the BAC during subjective satiety assessment. The control session will control for expectations of increased satiety with subsequent drinks. Control drinks contain cranberry juice with an alcohol mask (rim sprayed with vodka) matched in total volume to the alcohol drinks. Participants will be told that all drinks contain alcohol. Subjective response questionnaires are repeated 15 minutes after each drink. BACtrack S80 BrAC measures are repeated every 15 minutes.

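### Aim 5: the pre-alcohol HMGB1 sample is taken before the supplement and the planned regression has no term to absorb this; section 4.1 also misstates the sampling times

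*Combined protocol and SAP*

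**What the plan says.** Three places time the HMGB1 samples.

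- Section 4.1 (overview): "Blood fingerprick samples will be used to measure high-mobility group box 1 (HMGB1) inflammatory marker at three timepoints after alcohol administration".
- Section 3 (Aim 5 outcome): "via fingerprick at timepoints before alcohol administration, 30 minutes after an initial priming drink, and after the final drink".
- Section 4.3 (visit procedures): at arrival, alongside the baseline venipuncture, "Fingerprick blood sample will be used to measure HMGB1. Baseline measurements of study outcomes will be taken at this time". The supplement or placebo follows, then "Forty-five minutes after the dietary supplement, the second blood sample is taken. Next, a priming drink". A battery starts 15 minutes after priming, and the second fingerprick is its last listed item. The third follows the paced drinks.

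The schedule in section 1.2 lists three fingerpricks at each visit. The blood-sampling paragraph in section 4.3 repeats three timepoints without timing them.

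The supplement is crossed with placebo within person, in counterbalanced order over two visits. The paced drinks may be alcohol or control, but the plan does not say how these pair with supplement and placebo. The Aim 5 analysis in section 8.1 is a linear regression of HMGB1 on BrAC during the laboratory alcohol sessions. It names no other term.

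**The concern.** Aim 5 asks what acute alcohol does to HMGB1. The only alcohol-free sample in the procedures precedes the supplement, and no fingerprick falls between supplement and priming drink, although venous blood is already drawn at that point. The change from the first to the second sample therefore spans the supplement or placebo, a wait of at least 45 minutes, and the priming drink.

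BrAC is zero at arrival, because abstinence is checked by breathalyzer. It is expected to be positive at the second sample, and at the third when the paced drinks contain alcohol. Anything that moves HMGB1 after arrival thus moves with BrAC, and a regression on BrAC alone will credit part of it to alcohol. Section 4.1 adds a plain inconsistency about whether an alcohol-free sample exists. Both are easily settled before data collection; a sample not taken cannot be recovered afterwards.

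**Working it through.** **No figure to reproduce.** The plan gives no numerical target for Aim 5. The sample-size statement in section 8.2 (N = 42, 86% power) concerns within-between interactions and has no bearing here.

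**Sample counts.**

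| Source | Before alcohol | After alcohol | Total |
|---|---|---|---|
| Section 3, Aim 5 | 1 | 2 | 3 |
| Section 4.3, step by step | 1 | 2 | 3 |
| Section 1.2 | not timed | not timed | 3 |
| Section 4.1, read literally | 0 | 3 | 3 |

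Section 4.1 stands alone against the outcome definition and the procedures.

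**Length of the first interval.** From supplement to second fingerprick it is at least 45 + 15 = 60 minutes using the start of the battery in section 4.3, or 45 + 30 = 75 minutes using section 3. The part before alcohol is at least 45 minutes. This describes the clock only; it says nothing about the size of any bias.

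**How a shift reaches the slope.** Let x = BrAC/30, and let s = 1 for samples carrying a shift of δ units in HMGB1, otherwise 0. With true slope b, the expected slope from regressing HMGB1 on x alone is b + δ × Sxs/Sxx, where Sxx and Sxs are the corrected sums of squares and products.

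Assumed values: BrAC 0, 30, 65 mg% at the three samples when the paced drinks are alcohol (30 is the priming target; 65 is the midpoint of the planned 60-70) and 0, 30, 0 when they are control; b = 1; δ = 1 on both post-supplement samples at the supplement visit. So x = 0, 1, 2.167 or 0, 1, 0.

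| Pairing of paced drinks and supplement | Sxs | Sxx | Unadjusted slope |
|---|---|---|---|
| Alcohol at both visits | 1.056 | 4.704 | 1 + 0.224 = 1.22 |
| Alcohol/control crossed with supplement/placebo | 1.389 | 7.602 | 1 + 0.183 = 1.18 |
| Alcohol always with supplement | 1.778 | 3.801 | 1 + 0.468 = 1.47 |
| Alcohol always with placebo | -0.389 | 3.801 | 1 - 0.102 = 0.90 |

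A placebo visit with alcohol, analysed alone, gives 1.00. Adding a post-supplement term to the model gives 1.00 under every pairing, and so does δ = 0.

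**A shift common to both visits** (time in the lab, continued fasting). With alcohol at both visits and δ = 1 on both later samples of each visit, Sxs/Sxx = 2.111/4.704 = 0.449, so the slope is 1.45. A supplement term cannot remove this.

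**Moving the first sample to the 45-minute draw.** If the supplement shift is complete by then, s = 1 on all three samples at the supplement visit. Sxs is then 0 with alcohol at both visits or crossed, and the unadjusted slope is 1.00. If alcohol is always paired with the supplement, Sxs/Sxx = 1.083/3.801 = 0.285 and the slope is still 1.29 without a supplement term. Moving the sample helps but does not replace the model term.

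**The case against.** Four stronger readings are tempting, and the documents do not support them.

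*That Aim 5 has no baseline.* This follows only from the overview sentence. The outcome definition and the procedures both give a pre-alcohol sample, and staff at this single site would run visits from the procedures. It is a wording correction.

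*That alcohol and supplement effects cannot be separated.* The priming drink is scheduled at both visits, and a placebo option is described only for the later mini-drinks. Each person therefore has the same priming step once with supplement and once with placebo, and the between-visit difference in the first change estimates the supplement effect. This largely stands: the gap is a missing model term. The rescue is partial, because no such term is planned, because shifts common to both visits survive it, and because separation weakens after priming if alcohol is always paired with the supplement.

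*That 60-75% of the first change is contaminated.* Those percentages (45/75 and 45/60) are shares of minimum clock time. The second fingerprick ends a battery that only starts at 15 minutes, so the alcohol share is understated. From supplement to final sample, 45 minutes is 45/(45 + 15 + 120) = 25%.

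*That 15 and 30 minutes contradict each other.* A fingerprick at the end of a battery begun at 15 minutes can fall at 30.

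The other side also notes that the contrast between the second and third samples does not depend on the baseline, which is correct, and that a fasted arrival value has its own use: section 2.2 mentions individual differences in HMGB1. That is a real cost of moving the sample.

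**Conclusion.** The point holds in limited form. Section 4.1 conflicts with sections 3 and 4.3 and is probably a wording error. The scheduled baseline precedes the supplement by design, and the stated regression has nothing to absorb a supplement response or drift in the lab, so either can enter the BrAC slope. The counterbalanced placebo visit allows partial separation, but only if it is modelled.

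The magnitude is unknown. The documents give no effect of the supplement or of elapsed time on HMGB1, and if both are zero there is no bias. The illustrated slopes of 0.90 to 1.47 against a true 1.00 rest on an assumed one-unit shift, assumed BrAC values and an unstated pairing of drinks with supplement. They show direction and mechanism, not a forecast. The change is inexpensive and worth making before the first visit.

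**What to change.** 1. Correct section 4.1 to one sample before and two after alcohol.
2. Take the first fingerprick at the existing 45-minute post-supplement draw, just before the priming drink, and define it as the Aim 5 baseline.
3. State one clock time, relative to the priming drink, for the second fingerprick in sections 3 and 4.3.
4. Specify the Aim 5 model with supplement condition, visit/time and a participant random effect; each person contributes up to 3 × 2 = 6 samples, which are not independent.
5. State how alcohol/control drinks pair with supplement/placebo. If alcohol is drunk at both visits, BrAC and sample order rise together, and a time term leaves little but departures from target BrAC to identify the slope. Control paced drinks are what would make time separable, so the model cannot be settled until the pairing is.

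Cost: one existing fingerprick moves later in the visit, with no added sample. The fasted pre-supplement value is lost, although the moved sample at the placebo visit still gives a value free of active supplement for individual-differences work. A fourth fingerprick would keep both. If the arrival sample is retained as it is, the model terms in item 4 are the minimum correction.
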